Appendix 1 provides the Eligibility Checklist.

b. Procedures

Study overview: **Appendix 2** provides a schematic of the chronology of experimental procedures. The study will consist of a total of six visits.

Visit #1: Screening. Following a 20-minute phone screen with the parent and the child (**Appendix 3**), potentially eligible participants will be invited to the NIH for a screening visit to determine eligibility for the experimental portion of the study. The screening visit will be a half-day appointment. The following procedures will take place:

1. **Consent/assent.** Study purposes, all testing procedures, and possible study risks will be described in detail. Interested families will sign IRB-approved assent and consent forms (see also Consent/Accent Process, page 36).
2. **Brief history, physical exam, and body measurements** will be conducted by a trained practitioner (see **Appendix 4** for the screening visit physical exam form). A brief psychiatric and health history of the participant will be obtained from a parent or guardian in order to identify medical issues prior to study participation. This will include the assessment of current parental (guardian) medical and/or psychiatric illness, in addition to birth history of participants and factors associated with prenatal stress. Waist circumference (in cm) will be measured, as will pubertal development according to the stages of Tanner (103, 104). Tanner breast staging (by inspection and palpation) and pubic hair staging (by inspection) will be used to categorize youth as those in pre-puberty (Tanner stage 1), early to mid-puberty (Tanner stages 2–3), or late puberty (Tanner stages 4–5). In cases in which the stage is discordant between the right and left breasts, the higher stage will be assigned. Measurements of vital signs (blood pressure, pulse, and temperature) height in triplicate by stadiometer, and weight by calibrated scale will be conducted. BMI will be calculated as weight in kilograms divided by the square of height in meters (kg/m^2). BMI percentiles will be used to categorize participants as overweight ($\geq 85^{\text{th}}$ percentile) or obese ($\geq 95^{\text{th}}$ percentile) (105). A urine sample will be obtained from all participants and tested for pregnancy in postmenarcheal girls.

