3. **Whole body Dual-Energy X-ray Absorptiometry (DXA)** will assess fat, lean, and bone mass (Lunar iDXA, GE Healthcare) in a fasting state. DXA involves 0.003 mrem of radiation exposure per scan (total exposure for 3 scans: .0009 mrem).
4. **Youth Interviews.**
 - a. Eating Disorder Examination (EDE), Version 14 (106) (see **Appendix 5**) or the EDE adapted for children (children age < 14 years) (107) is a semi-structured psychodiagnostic interview of eating disorder psychopathology. The EDE is the “gold

standard” interview for diagnosing disordered eating. The overeating section will be administered to determine LOC presence and severity. The EDE is reliable and valid in adolescent samples (38, 59, 108, 109). Participants who report at least one episode of LOC eating in the past 28 days on the EDE, will be assigned to the LOC group. Participants who deny LOC episodes in the past 28 days will be assigned to the non-LOC group.

b. Physical Activity. To determine the average amount of moderate-to-vigorous physical activity each participant has engaged in within the previous week, children will be asked two items from the International Physical Activity Questionnaire (IPAQ) screening form (110). These data will be used to help determine the amount of the standardized breakfast shake for each participant in subsequent visits. See **Appendix 6** for the list of items.

5. **Youth Questionnaires.** Youth will complete a battery of self-report questionnaires including the following (see **Appendix 6** for the measures):

- a. Beck Depression Inventory (BDI) (111) is a widely used valid and reliable (112) questionnaire that measures self-reported severity of depressive symptoms. It has been shown to be internally consistent (alphas = .86 for psychiatric patients and .81 for nonpsychiatric subjects). Concurrent validity with other measures of depression for psychiatric patients has ranged between .72 and .73 and for nonpsychiatric individuals between .60 and .74. If participant endorses a positive screen ($BDI \geq 20$), she will be further assessed for depression symptoms according to the DSM-5 criteria using a semi-structured interview (see *Supplemental Assessment* section below). Only girls who are at least 14-years-old will complete the BDI.
- b. Children’s Depression Inventory (CDI) (113, 114) assesses the presence and degree of childhood depressive symptoms and is a widely used measure with very good reliability and validity.

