Visit #2: Baseline Laboratory Session. The baseline lab will be scheduled within a week of the screening session. The baseline lab visit will be a half-day appointment that starts in the morning (from approx. 8AM to 1PM). Participants will be instructed to engage in an overnight fast starting at 10:00PM the night prior to the visit. The following procedures will take place:

1. **Phlebotomy.** Blood will be drawn from participants by a phlebotomist or registered nurse for obesity-related measurements (e.g., acute care panel, hepatic panel, lipid panel, mineral panel, insulin, c-peptide, glycosylated hemoglobin, TSH, free T4, ESR, hsCRP), appetite-regulating hormones (e.g., leptin, ghrelin, oxytocin), nutritional status (e.g., 25-hydroxyvitamin D, iron), and hematological status (e.g., CBC), and samples to save for future research (75 mL). If desired, we will use ELA-Max cream so that the blood draw will hurt less. Total blood withdrawal will be within NIH pediatric guidelines (3.5mL/kg

per single draw, 7 mL/kg per 6 weeks) since participants will have minimum age 12y and will be eligible to join the study only if BMI exceeds the 85th percentile for age (BMI must be more than 20.9 kg/m²), weight will always exceed 40 kg; thus up to 140 cc may be obtained at a single blood draw.

2. **Standard breakfast shake.** Participants will receive a standard breakfast shake, the amount of which (21% of estimated daily energy needs) is determined by measured body weight, height, age and average activity level in the previous week. The shake will consist of 17% protein, 16% fat and 67% carbohydrate. This is a standardized procedure to reduce the effect of hunger on AB to food. If the participant has lactose intolerance, lactase pills will be administered at the beginning of the visit or a lactose-free shake will be offered.

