second session, participants will be asked to return for a brief visit to perform the anatomical MRI scan. Contingent on the availability of the scanner, the participants may be scheduled to complete the anatomical MRI on a day separate from their study visit. They will be compensated for their time. A urine sample will be obtained from all participants and tested for pregnancy on the day of the participant's anatomical MRI scan. If a participant has undergone an anatomical MRI scan at the NIH of sufficient quality in the preceding two months, she will not be required to complete another MRI anatomical scan as part of this study.

7. **Smartphone training.** Participants will be given the mobile devices with attention retraining or the control program. Before they leave the laboratory, they will be trained in the use of the mobile devices and provided with contact information of the study staff to aid with troubleshooting of any problems that might arise. The training will take approximately 20 minutes.

Attention Retraining or Control Program with Ecological Momentary Assessment (EMA) in the Natural Environment for 2 Weeks. Participants will be randomized in blocks of 8 with stratification for LOC status (LOC vs. no-LOC), race/ethnicity (Hispanic/Non-Hispanic, Black/White), and age (12-14; >14) to attention retraining or control programs carefully matched for intensity of interaction. In addition to three attention retraining or control trials administered on the smartphone each day, attention bias will be assessed once a day. Each of the four daily trials will also include an EMA component in which participants answer questions regarding their eating patterns and mood in real time. A sample administration schedule for a school day is presented in Figure 3.

Figure 3. Sample administration schedule.

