Specific Aim 2: Examine changes in neural responsivity following a 2-week attention retraining or control period.

- i. **Primary outcomes:** Change in neural activity during attention bias task paradigm at the baseline laboratory visit vs. post-EMA visit.
- ii. **Secondary outcomes:** Neural activity during the social threat AB task.

Specific Aim 3: Examine the effect of attention retraining on food intake and body composition.

- i. **Primary outcomes:** Change in the energy intake at the buffet meal, change in adiposity/body composition (DXA) from the baseline visit to the post-EMA visit.
- ii. **Secondary outcomes:** Change in self-reported eating patterns (EDE), number of LOC episodes measured via EMA and clinical interview,

Exploratory Aim 1: Examine whether dose-response effects are present for attention bias to palatable foods and body composition in participants who receive the attention retraining program at 3 months as a booster compared to those who receive it for the first time.

- i. **Primary outcomes:** Change in laboratory measured attention bias (i.e., reaction times to palatable foods at the baseline laboratory visit vs. the post-EMA visit), adiposity/body composition (DXA)
- ii. **Secondary outcomes:** Change in EMA-measured attention bias over time (2-week period), self-reported eating patterns (EDE), number of LOC episodes measured via EMA and clinical interview.

Exploratory Aim 2: Examine ABs to social threat (measured as reaction time, eye tracking, and neural activation on the AB to social threat visual probe task at baseline), and potential moderating effects of AB to social threat on intervention effects.

- i. **Outcomes:** Change in energy intake at the buffet meal, adiposity/body composition (DXA).

Exploratory Aim 3: Examine LOC status (LOC vs. No-LOC) on primary outcomes.

- i. **Outcomes:** Change in neural activity during attention bias task paradigm at the baseline laboratory visit vs. post-EMA visit, change in laboratory measured attention bias (i.e., reaction times to palatable foods at the baseline laboratory visit vs. the post-EMA visit), change in food intake, change in adiposity/body composition (DXA)

Exploratory Aim 4: Examine effects of race on primary outcomes.

- a. **Outcomes:** Laboratory measured attention bias (i.e., reaction times to palatable foods at the baseline laboratory visit vs. the post-EMA visit), the energy intake at the buffet meal, adiposity/body composition (DXA).

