1. Post-smartphone program lab visit and the 3-month follow-up visit reaction time data from dot probe task will be using a general linear model (or appropriate generalized linear model depending upon distribution diagnostics) controlling for baseline visit reaction time data from dot probe task, and covariates (order effects, age, race, and BMIZ).
2. Reaction time data from EMA

Specific Aim 2

- a. **Hypothesis 2:** General linear model adjusting for baseline neural activity and covariates (order effects, age, race, and BMIZ), will be used to analyze

1. Post-smartphone visit and 3-month follow-up visit neural activity in response to palatable food cues in the “bottom-up” attention circuitry (ventral ACC, OFC, insula, and striatum) in the unconscious reaction period.
2. Post-smartphone visit and 3-month follow-up visit neural activity in response to palatable food cues in the “top-down” attention circuitry (dorsal ACC, vLPFC, dlPFC) in the attention deployment period.

Specific Aim 3

- a. **Hypothesis 3A:** Youth randomized to AR and control groups will be compared on
 1. Post-smartphone program lab energy intake from laboratory test meal using a general linear model (or appropriate generalized linear model depending upon distribution diagnostics) controlling for the baseline visit energy intake and covariates
 2. The daily number of LOC episodes using a generalized estimating equations (GEE) model with a negative binomial response function controlling for baseline LOC episodes and covariates. The model will include a main effect for group, and a group-by-time interaction. Analyses use all available data (no imputation). We will also examine LOC as a continuous daily dependent variable (mean of 3 LOC items).
 3. BMI and adiposity at the 3-month follow-up visit using a general linear model (or appropriate generalized linear model depending upon distribution diagnostics) controlling for baseline lab visit and the post-smartphone program lab visit BMI and adiposity.

Exploratory Aim 1

- a. Youth randomized to AR (who receive the AR program at 3 months as a booster) will be compared to controls (who receive AR for the first time) at post-booster visit and the 6-month follow-up visit on BMI, adiposity, and energy intake using a general linear model (or appropriate generalized linear model depending upon distribution diagnostics) controlling for Visit #2 measurement

Exploratory Aim 2

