5. **Radiation exposure.** This research study involves exposure to radiation from three DXA scans (at baseline, 3-months, and 6-months). This radiation exposure is not necessary for medical care and is for research purposes only. Although each organ will receive a different dose, the total amount of radiation exposure participants will receive yearly from this study each year is equal to a uniform whole-body exposure of 0.009 mrem for child subjects. This calculated value is known as the "effective dose" and is used to relate the dose received by each organ to a single value. The amount of radiation participants will receive in this study is well below the dose guideline established by the NIH Radiation Safety Committee for child (less than 500 mrem per year) or adult (less than 5000 mrem per year) research subjects. For comparison, the average person in the United States receives a radiation exposure of 300 mrem per year from natural background sources, such as from the sun, outer space, and from radioactive materials that are found naturally in the earth's air and soil. The effective dose that participants will receive from participation in this research study is less than the amount normally received in one day from these natural sources. For more information about radiation and examples of exposure levels from other sources, participants will, upon request, be given a copy of the pamphlet called, *An Introduction to Radiation for NIH Research Subjects*. This protocol has been submitted for approval by the Radiation Safety Committee.
6. **Urine collection** methods involve no risk but may be inconvenient because of the time required for collection. If participants have difficulty voiding, they will be offered water and asked to try again at a later time. Parents will be informed that girls who are found to be pregnant become emancipated minors for the purpose of health care decision-making, and that the child, not the parent, will be told about a positive pregnancy test.

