scheduled to be administered. When conducting feeding studies, participants may suffer from food allergies that restrict the types of foods they are able to eat. If the participant has lactose intolerance, lactase pills will be administered at the beginning of the visit. Similarly, certain ethical and religious beliefs may limit participants from eating foods on the array. In these cases, we will substitute foods that are of equivalent nutritional value and within the same food group. The proposed study will be carried out at the NIH CRC, where there are ample medical resources (including the NIH critical care team) should an unanticipated event occur. Metabolic cooks preparing and measuring foods for test meals have yearly HACCP food safety training that focuses upon safe food handling, proper temperatures, hand washing, and using gloves when handling food. All dietitians also have had training in weighing/processing foods for controlled feeding studies to ensure consistency in the method and presentation.

12. **Time required.** Time commitment will vary depending on the parts of the study participants decide to participate in, as well as eligibility. The screening visit (Visit #1) requires approximately 5 hours on the part of the study participant and their parent/guardian. If they are eligible following this visit, youth will be asked to return to the NIH CRC within one week for a baseline laboratory session (Visit #2) to participate in the attention bias and MEG component of the protocol. This visit will take approximately 4 hours to complete. At the end of that visit, youth will receive instructions on completing the attention training and EMA portion of the protocol using the smartphones. For that portion of this protocol, youth will be asked to respond to various prompts on their smartphones 4x/day for approximately 5 minutes, for 14 days. Estimated time required to respond to all of these prompts is 20 minutes per day (for a total of 280 min or nearly 5 hours). Time commitment for the post-EMA visit (Visit #3) is approximately 4 hours, 4 hours for follow-up 1 (Visit #4), and 4 hours for follow-up #3 (Visit #6).

Participants and their parents/guardians will be informed in detail of all potential risks during the informed consent/assent process.

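### Aim 3's primary DXA outcome ends at a visit with no DXA scan, and the 3-month body-composition model adjusts for values from that same post-randomisation visit

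*Combined protocol and SAP*

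**What the plan says.** Section VII.c (Primary Outcomes, Specific Aim 3) lists as a primary outcome "change in adiposity/body composition (DXA) from the baseline visit to the post-EMA visit". Section VIII.d (Risks, item 12, Time required) identifies that visit: "Time commitment for the post-EMA visit (Visit #3) is approximately 4 hours".

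Section VII.f (Primary Analyses, Specific Aim 3, item 3) analyses BMI and adiposity at the 3-month follow-up with a general linear model, "controlling for baseline lab visit and the post-smartphone program lab visit BMI and adiposity".

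On when DXA is done, section VI.b describes it at Visit 1, where it "will assess fat, lean, and bone mass (Lunar iDXA, GE Healthcare) in a fasting state", and lists it again at Visits 4 and 6. Section VIII.d (item 5, Radiation exposure) confirms the total: "three DXA scans (at baseline, 3-months, and 6-months".

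On order in time, the phones are handed over at the end of Visit 2: "Participants will be given the mobile devices with attention retraining or the control program". Visit 3 follows two weeks later, when the randomised program ends. Its list contains BMI and waist circumference, the MEG and attention tasks, and the test meal.

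Hypothesis 3B in section V concerns weight gain and adiposity at the 3-month follow-up, which is Visit 4.

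**The concern.** Three things do not fit together.

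- **DXA outcome.** A named primary outcome ends at a visit where no scan is planned. The 3-month DXA model also needs a covariate from that visit. Neither can be computed.
- **BMI model.** Visit 3 BMI is available, but it is measured after two weeks of randomised treatment. Adjusting for it removes part of any effect already present, so the arm coefficient is not the total between-arm difference that Hypothesis 3B describes.
- **Baseline label.** The model takes its baseline from the baseline lab visit, which is Visit 2. Neither BMI nor DXA is listed there. Both belong to Visit 1, where "BMI will be calculated as weight in kilograms divided by the square of height in meters". The gap can be up to a week: "The baseline lab will be scheduled within a week of the screening session".

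If the text stays as it is, the end visit and covariates of a primary outcome would have to be settled later, possibly with data in hand.

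**Working it through.** **Step 1. Reproduce the scan count.** From the visit lists in VI.b:

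| Visit | BMI | DXA | Test meal |
|---|---|---|---|
| 1 Screening | yes | yes | no |
| 2 Baseline lab | not listed | no | yes |
| 3 Post-program | yes | **no** | yes |
| 4 Three months | yes | yes | yes |
| 5 Post-booster | yes | no | no |
| 6 Six months | yes | yes | yes |

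That gives three scans, as VIII.d states. The stated exposure agrees: 3 × 0.003 = 0.009 mrem. A Visit 3 scan would be a fourth.

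**Step 2. DXA outcome and model.** Scheduled Visit 3 DXA values: 0 of 80. Complete cases for the change score are therefore 0, as they are for a model with Visit 3 DXA as a covariate. VII.f plans multiple imputation for non-EMA assessments, but an imputation model for a variable observed in no one has nothing to be estimated from. As a check, 80 simulated participants had Visit 1 DXA, Visit 3 BMI and Visit 4 DXA, with Visit 3 DXA absent for all. The chained-equation routine stopped because the variable had no observed values.

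**Step 3. What Visit 3 adjustment does for BMI.** Let D be the total 3-month effect, f the share of D present at Visit 3, b the slope of 3-month BMI on Visit 3 BMI given baseline, and c the arm coefficient in the adjusted model. Arm is independent of baseline by randomisation, so

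D = c + b × (f × D), hence c = D × (1 − b × f).

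The documents give neither f nor b, so both are assumed over a range. The even-accrual case takes Visit 3 at 2 weeks and Visit 4 about 13 weeks after that: f = 2/15. For example, with b = 0.75, 1 − 0.75 × 2/15 = 0.90.

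Share of the total effect kept:

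| f | b = 0.5 | b = 0.75 | b = 1 |
|---|---|---|---|
| 0 | 100% | 100% | 100% |
| 2/15 | 93.3% | 90.0% | 86.7% |
| 0.25 | 87.5% | 81.2% | 75.0% |
| 0.5 | 75.0% | 62.5% | 50.0% |
| 1 | 50% | 25% | 0% |

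The range for b is plausible. With equal variances and assumed correlations of 0.90 (baseline–Visit 3), 0.80 (baseline–Visit 4) and 0.85 (Visit 3–Visit 4), b = (0.85 − 0.90 × 0.80)/(1 − 0.90²) = 0.13/0.19 = 0.68. With 0.99, 0.97 and 0.98, b = 0.0197/0.0199 = 0.99.

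A simulation with 400,000 participants per cell and an assumed total effect of −0.50 kg/m² agrees. The baseline-only model returned −0.493 to −0.503 throughout. With Visit 3 BMI added and b = 1, the estimates were −0.431 at f = 2/15, −0.250 at f = 0.5 and 0.001 at f = 1.

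**Step 4. Which visit was meant.** Hypothesis 3B, the Visit 4 description, the outcome visit in the VII.f model and Exploratory Aim 3 in VII.f all place body composition at 3 months. VII.c alone gives a different outcome visit. The VII.f covariate, however, also presumes a Visit 3 adiposity value, so two places need changing.

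**Step 5. A lesser related point.** Exploratory Aim 1 in VII.f compares adiposity and energy intake at the post-booster visit (Visit 5), where neither DXA nor a test meal is listed. It adjusts for a Visit 2 measurement, which is listed for energy intake but not for BMI or DXA.

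**The case against.** The best defence is that there is one evident resolution. Visit 1 is the only scan before randomisation, Visit 4 is the only later scan before all girls are offered retraining, and most of the plan points to 3 months. The study calls itself a pilot and its sample size rests on Aim 1. This is fair: the repair is easy and little is open to choice for DXA. It does not make the written primary outcome computable.

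Other readings were considered:

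- VI.b introduces Visit 3 as combining procedures from Visits 1 and 2. An explicit list without DXA follows, and the three-scan total leaves no room for one.
- Adiposity is not defined in VII.f item 3 and could mean waist circumference, which Visit 3 does measure. VII.c ties adiposity to DXA. Even on the other reading, the VII.c outcome would remain uncomputable and Visit 3 waist would still be post-randomisation.
- The post-EMA visit might mean Visit 5, but no DXA is listed there either.

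On BMI the objection carries more weight. The model can be fitted and gives a legitimate conditional estimate. Under even accrual the loss is modest, and nothing in the documents suggests that half or all of a 3-month BMI effect appears within two weeks. The reaction-time and neural models adjust only for the baseline value of their outcome, but that is weak evidence of inconsistency, because Visit 3 is itself an outcome visit there.

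The baseline label is the mildest part. VIII.d already calls the first DXA the baseline scan, and the Visit 2 breakfast shake is sized from measured weight and height without saying when they were measured.

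**Conclusion.** The concern holds. For DXA it rests on the documents alone: 0 of 80 girls have a scheduled Visit 3 scan, so a primary outcome and the DXA form of its model cannot be run as written. This is why the text must be corrected.

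For BMI, the adjusted coefficient is not the total effect in Hypothesis 3B, but no bias of known size is shown. The loss is zero if retraining has no BMI effect by Visit 3, and about 7% to 13% under even accrual with b between 0.5 and 1. Larger losses need values of f for which the documents give no support. The baseline label and the Exploratory Aim 1 visits are lesser points of wording.

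**What to change.** 1. **VII.c, Specific Aim 3.** Restate the body-composition primary outcome as change in DXA adiposity from Visit 1 to Visit 4. BMI can stay where it is, in the VII.f analyses, and need not be added to this outcome.
2. **VII.f, Specific Aim 3, item 3.** Among the BMI and adiposity covariates, keep only pre-randomisation values, and state that they come from Visit 1. A BMI model that also includes Visit 3 BMI may remain as a labelled secondary analysis.
3. **VII.f, Exploratory Aim 1.** Analyse DXA adiposity and energy intake at Visit 6 only. Name Visit 1 as the adjustment visit for BMI and DXA, and Visit 2 for energy intake.

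The cost is wording only, with no new visit, scan or participant. The change should be made before outcome data are examined by arm.
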